**Table 1: Demographic data and comorbidities of the studied groups**

		Group 1 (n=45)	Group 2 (n=45)	P value	Mean difference or RR (95% CI)
Age (years)	Mean <math>\pm</math> SD	62.76 $\pm$ 8.16	65.58 $\pm$ 7.98	0.101	-2.82(-6.2: 0.56)
	Range	46 - 85	50 - 83		
Diabetes mellitus	9 (20%)	7 (15.56%)	0.581	1.29(0.52:3.15)	
Hypertension	10 (22.22%)	10 (22.22%)	1	1(0.46:2.17)	
Ischemic heart disease	2 (4.44%)	0 (0%)	0.153	---	

CI: Confidence interval, RR: Relative risk

Age, diabetes mellitus, hypertension and ischemic heart disease were insignificantly different between two groups.

**Figure 2: Age of the studied groups.**

[figure not shown]
**Figure 3:** Comorbidities of the studied groups.

**Table 2: IPSS score of the studied groups**

	Group 1 (n=43)	Group 2 (n=41)	P value	Mean difference (95% CI)
Preoperative (0-35)	26.58±3.65	28.42±3.2	0.013*	-1.84(-3.28: -0.406)
3 months postoperative	7.14±2.99	6.68±2.43	0.446	0.456(-0.729: 1.642)
6 months postoperative	5.12±2.62	4.07±3.38	0.117	1.043(-0.265:2.352)

\*Significantly different as P value  $\leq 0.05$ , CI: Confidence interval, IPSS: International prostate symptom Score

IPSS score was significantly lower at preoperative (0-35) in group 1 than group 2 as (P value = 0.013) and was insignificantly different at (3 and 6 months) postoperative between both groups.

[figure not shown]

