More recently, a better understanding of ejaculation physiology has enabled the emergence of modified surgical techniques with the aim of preserving antegrade ejaculation [13–16].

The key point of standard TURP is resecting the tissues enveloped in the prostatic capsule and the bladder neck, while protecting the urethral tissues below the verumontanum [17].

The bladder neck plays a significant role in reproduction. For men, bladder neck closure facilitates anterograde ejaculation. It actively contracts the bladder neck during ejaculation through a rich noradrenergic innervation by sympathetic nerves [18].

Vernet et al. showed that contraction of the bladder neck was not important for anterograde ejaculation [19]. Using endorectal ultrasound videos performed during masturbation in 30 men, it was possible to visualize the bladder neck, the prostate, and the bulbar urethra during ejaculation. They observed that during ejaculation, the verumontanum underwent a slight

caudal shift, momentarily making contact with the opposite urethral wall and sperm emitted from the ejaculatory ducts was directed distally by contractions of the external sphincter coordinated with contractions of the bulbar urethra, thus demonstrating the importance of the muscular tissue around the verumontanum and particularly its proximal part. They described this area as a “high-pressure ejaculatory area”. The closure of the bladder neck did not seem to play a role in this mechanism. As a result, one can conclude that as long as the tissues around the verumontanum are not injured, ejaculation should still occur even with a well-open bladder neck [20].

Recently, together with a better understanding of the mechanisms of ejaculation, a greater importance has been given to the impact of dry ejaculation on patients’ QoL [21]. A balance between symptomatic improvement in LUTS and preservation of sexual function needs to be addressed for men seeking surgical treatment [22].

Modifications based on Supramontanal sparing hypothesis have reported favorable outcomes to as high as 92% [23].

Although preservation of bladder neck structures is often associated with preservation of antegrade ejaculation, the current modern approach is the preservation of the precollicular and para-collicular tissue in the area where the ejaculatory ducts emerge near the verumontanum in the distal apical tissue in laser, aquablation, and bipolar electrosurgical prostatectomy techniques [24].

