### **Aim of the work:**

The purpose of this study is to assess the outcomes and efficacy of ejaculatory preserving TURP in terms of voiding, erectile function, and ejaculation.

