**-Type of the study:**

A prospective comparative study.

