**Surgical Technique:**

Cystoscopy will be conducted under spinal anaesthesia with a 30° telescope and the patient in dorsal lithotomy posture. Eligible patients will be randomly assigned to one of two groups with double blind evaluation. Group 1 will have ejaculatory preserving TURP, whereas Group 2 will

have traditional TURP. Randomization will be done by computer programming such as SAS. The Operators will be the supervisors of the principle investigator.

All procedures will be carried out with bipolar-flow 26 Fr bipolar resectoscopes (Karl-Storz, Germany) configured for resection in 0.9% saline solution and cut/coagulation set at 130/70 W.

In Group 1, resection of lateral lobes to the capsule and the ventral side to the level of the verumontanum with avoidance of paracollicular digging. Circular resection of the internal bladder neck will be done. Then the next step will be apical resection utilizing the colliculus seminalis as a distal resection border and maintaining a 1 cm safety area for preservation of ejaculation.

In Group 2, the whole adenoma tissue, including the tissue in front of the verumontanum and bladder neck, will be removed to the prostatic capsule.

After full hemostasis, a 20 Fr three-way catheter will be placed into the bladder, traction will be performed, and the bladder will be irrigated with 0.9% saline postoperatively until clear effluent is seen.

The patient will be discharged from the hospital on the next postoperative day. Sexual activity will be prohibited for 6 weeks following the intervention.

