**Statistical analysis:**

Statistical analysis was done by SPSS v26 (IBM Inc., Chicago, IL, USA). Shapiro-Wilks test and histograms were used to evaluate the normality of the distribution of data. Quantitative parametric variables were presented as mean and standard deviation (SD) and compared between the two groups utilizing unpaired Student's T- test. Quantitative non-parametric data were presented as median and interquartile range (IQR) and were analyzed by Mann-Whitney test. Qualitative variables were presented as frequency and percentage and were analyzed utilizing the Chi-square test or Fisher's exact test when appropriate. A two tailed P value  $< 0.05$  was considered statistically significant

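### Voiding outcomes are tested only for a difference, with no margin, so non-significant IPSS (3 and 6 months) and Qmax (6 months) cannot be read as preserved voiding efficacy

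*Combined protocol and SAP*

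**What the plan says.** The Aim of the work is "to assess the outcomes and efficacy of ejaculatory preserving TURP in terms of voiding, erectile function, and ejaculation". The Introduction presents standard TURP as the established treatment with proven efficacy and ejaculatory loss as its drawback, and says: "A balance between symptomatic improvement in LUTS and preservation of sexual function needs to be addressed for men seeking surgical treatment". The Type of the study entry says only "A prospective comparative study". Under Surgical Technique, Group 1 keeps a 1 cm safety zone near the verumontanum, while Group 2 has all the adenoma removed.

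The Statistical analysis section gives one rule for all normally distributed quantitative outcomes: they are "compared between the two groups utilizing unpaired Student's T- test". Significance is "A two tailed P value" below 0.05. No margin, equivalence test, primary endpoint or sample-size rationale appears anywhere.

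The text under Table 2 says that IPSS "was insignificantly different at (3 and 6 months) postoperative between both groups". The text under Table 7 reports 6-month Qmax as not significantly different. It reports 3-month Qmax as significantly lower, and PVR at both visits as significantly higher, in Group 1. Each comparison has a 95% interval printed beside it.

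**The concern.** The trial sets a technique that leaves tissue behind against the accepted voiding treatment. For ejaculation, a test of superiority fits. For voiding, the question a surgeon or patient would naturally ask is whether the new technique is materially worse. A two-sided difference test without a margin cannot answer that: P > 0.05 can mean that there is little difference, or that the data are too imprecise to show one.

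What is at stake is the voiding half of the trade-off. A reader who meets non-significant IPSS and 6-month Qmax may take them as reassurance that nothing was lost. IPSS and Qmax get the same verdict although their intervals differ in what they exclude. The IPSS comparison also takes no account of a significant baseline imbalance.

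**Working it through.** **Inputs.** Means and SDs from Table 2 (IPSS) and Table 7 (Qmax), with n = 43 and 41 from the table headers. Differences are Group 1 minus Group 2. Higher IPSS and lower Qmax are worse.

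**1. Reproduce the printed intervals.** Pooled SD s = √[(42·s₁² + 40·s₂²)/82]; SE = s·√(1/43 + 1/41); 95% CI = difference ± t(82)·SE.

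| Outcome | s | SE | Recomputed | Printed |
|---|---|---|---|---|
| IPSS 3 months | 2.73 | 0.596 | 0.46 (-0.73 to 1.65), P = 0.443 | 0.456 (-0.729 to 1.642), P = 0.446 |
| IPSS 6 months | 3.01 | 0.658 | 1.05 (-0.26 to 2.36), P = 0.114 | 1.043 (-0.265 to 2.352), P = 0.117 |
| Qmax 3 months | 4.70 | 1.026 | -2.69 (-4.73 to -0.65), P = 0.0105 | -2.696 (-4.738 to -0.654), P = 0.01 |
| Qmax 6 months | 5.70 | 1.245 | -0.93 (-3.41 to 1.55), P = 0.457 | -0.93 (-3.407 to 1.55), P = 0.457 |

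All agree within rounding. At 6 months the worse limits are 2.4 IPSS points and 3.4 mL/s.

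**2. What the difference test could detect for Qmax at 6 months.** Power ≈ Φ(loss/1.245 − 1.96).

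- True loss 2 mL/s: Φ(−0.35) = 0.36, so about 64% of such trials would report no significant difference.
- 2.4 mL/s: 0.49.
- 3 mL/s: 0.67.
- 3.5 mL/s: 0.80.

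The chance of missing a loss falls below one half from about 1.96 × 1.245 = 2.4 mL/s upward.

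**3. Baseline IPSS.** Table 2 gives 26.58 vs 28.42, difference -1.84 (-3.28 to -0.406), P = 0.013. From the printed means, the fall to 6 months is 26.58 − 5.12 = 21.46 in Group 1 and 28.42 − 4.07 = 24.35 in Group 2. That is 2.89 points less in Group 1, against 1.05 on the raw 6-month scores.

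The documents do not give the correlation r between baseline and 6-month IPSS, so a range is assumed. Within-group slope b = r × 3.015/3.438 = 0.877r. Adjusted difference = 1.05 + 1.84b. SE = 3.015·√[(1 − r²)·82/81]·√[1/43 + 1/41 + 1.84²/(82 × 3.438²)], with t on 81 df.

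| Assumed r | Adjusted difference | 95% CI |
|---|---|---|
| 0.1 | 1.21 | -0.15 to 2.57 |
| 0.2 | 1.37 | 0.04 to 2.71 |
| 0.3 | 1.53 | 0.23 to 2.84 |
| 0.5 | 1.86 | 0.68 to 3.04 |

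The upper limit moves to about 2.6 to 3.0 points. From r of about 0.2 the difference would be significant against Group 1. This treats the printed baseline means as those of the 43 and 41 men analysed. The printed baseline interval in fact fits 45 and 45 (-3.28 to -0.40) rather than 43 and 41 (-3.33 to -0.35), so the result is approximate.

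**4. The other voiding results (Table 7).** Qmax at 3 months is 2.70 mL/s lower in Group 1. PVR medians at 6 months are 49 vs 34 mL, P < 0.001. The PVR interval is printed as -21 (-29 to -12). Given the medians and the text, this means 12 to 29 mL higher in Group 1. At 3 months PVR is also higher in Group 1 (55 vs 39 mL, P = 0.003).

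**The case against.** The strongest reply is that the plan sets out to compare and does so. The stated aim is to assess outcomes, and a balance can be studied by estimating a voiding cost as well as by ruling one out. The results wording reports a test outcome with its interval alongside, and similar wording is used for age and haemoglobin. Much of this stands, and it limits how far the point goes. Five stronger readings are tempting, and the documents do not support them.

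- **That the trial had a non-inferiority objective and failed to test it.** None is stated. It is a reasonable inference from the Introduction and the two techniques, no more.
- **That the documents claim equal voiding efficacy.** They do not. The risk lies in how the results are read and later summarised.
- **That the planned tests could not reveal worse voiding.** They did: 3-month Qmax and PVR at both visits are reported as significantly worse in Group 1.
- **That a real loss of flow would most likely be missed.** This holds only for true losses below about 2.4 mL/s.
- **That the IPSS interval is favourable, or passes a margin.** It ignores Group 1's lower baseline, and there is no stated margin to pass. A margin chosen now, with the data in view, could be picked to give either answer, and labelling it post hoc would not cure that.

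What the reply does not remove is that three voiding comparisons rest on significance wording that cannot show efficacy was kept.

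**Conclusion.** The point holds as a limit on interpretation. With difference tests only and no margin, non-significant IPSS at 3 and 6 months and Qmax at 6 months are not evidence of preserved or equal voiding. At 6 months the data leave open a Qmax loss of up to 3.4 mL/s and an unadjusted IPSS up to 2.4 points worse. Under the assumed correlations, baseline adjustment raises that IPSS limit and may make the difference itself significant. Together with 3-month Qmax and PVR, the voiding results lean against Group 1.

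The unadjusted limits rest only on printed figures. The adjusted ones rest on the assumed correlation and on the printed baseline means applying to the men analysed.

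**What to change.** 1. In the text under Tables 2 and 7, replace the significance wording for voiding with what the intervals leave open: at 6 months, a Qmax loss of up to 3.4 mL/s in Group 1 is not excluded, and unadjusted IPSS may be up to 2.4 points worse.
2. Report 6-month and 3-month IPSS adjusted for baseline (a linear model with group and baseline IPSS), and base any IPSS statement on that interval. State the number of men behind each row of Table 2.
3. Present these together with 3-month Qmax (-2.70 mL/s, -4.74 to -0.65) and PVR at both visits (6 months: 12 to 29 mL higher in Group 1). In the same edit, reconcile the 3-month Qmax P value, which is 0.01 in Table 7 and 0.03 in the text; the printed means and SDs give 0.0105.
4. In the Statistical analysis section, add one sentence saying that no margin was set in advance and that non-significance is not evidence of equal voiding efficacy.
5. Keep the superiority test for preserved ejaculation. Do not add a non-inferiority test with a margin chosen after the data.

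Cost: rewording and one regression on data already held. The downside is that the voiding statement becomes less favourable to the sparing technique.

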**Figure 4: IPSS score of the studied groups.**

**Table 3: IIEF-5Q score of the studied groups**

	Group 1 (n=43)	Group 2 (n=41)	P value	Mean difference (95% CI)
Preoperative (5-25)	19.76±2.64	20.04±2.45	0.592	-0.289(-1.354: 0.776)
3 months postoperative	20.14±2.58	18.41±2.49	0.003*	1.725(0.624:2.826)
6 months postoperative	20.05±3.11	17.78±2.96	<0.001*	2.266(0.947: 3.585)

\*Significantly different as P value  $\leq 0.05$ , CI: Confidence interval, IIEF-5Q: International index of erectile function – 5-question version

IIEF-5Q score was insignificantly different at preoperative (5-25) between both groups and was significantly higher at 3 and 6 months postoperative in group 1 than in group 2 (P value  $<0.05$ ).

[figure not shown]
**Figure 5: IIEF-5Q of the studied groups.**

**Table 4: MSHQ-EjD score of the studied groups**

	Group 1 (n=43)	Group 2 (n=41)	P value	Mean difference (95% CI)
Preoperative (1-15)	12.42±1.23	10.98±2.16	<0.001*	1.44(0.708: 2.181)
3 months postoperative	10.26±1.42	9.63±1.77	0.284	0.632(-0.544: 1.808)
6 months postoperative	10.62±1.76	10.38±2.26	0.741	0.243(-1.232: 1.717)

\*Significantly different as P value  $\leq 0.05$ , CI: Confidence interval, MSHQ-EjD: Male sexual health questionnaire – ejaculatory dysfunction short form, TTT: Treatment

MSHQ-EjD score was significantly higher at preoperative (1-15) in group 1 than group 2 (P value <0.001) and was insignificantly different at three and six months postoperative between both groups.

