#### **Follow up:**

All patients will be followed-up regularly at 3 and 6 months postoperatively with the IPSS, Qmax, PVR, IIEF-5Q, MSHQ-EjD Short Form, and rates of complications (including urethral stricture, incontinence, bladder neck contracture, Recatheterisation, UTI, and retrograde ejaculation).

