## Results

In this study, 103 patients were assessed for eligibility; 8 patients did not meet the criteria and 5 patients refused to participate in the study. The remaining patients were randomly allocated into two equal groups (45 patients in each). All allocated patients were followed-up and analyzed statistically (**Figure 42**).

[figure not shown]

[figure not shown]
Figure 1: CONSORT flow chart of the enrolled patients.

[figure not shown]

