**Figure 16: Complications of the studied groups.**

**Table 10: Post-operative preserved ejaculation, semen volume and concentration of the studied groups**

[figure not shown]
		Group 1 (n=43)	Group 2 (n=41)	P value	Median, mean difference or RR (95% CI)
Preserved ejaculation	After 3 months	35 (81.4%)	8 (19.51%)	<0.001*	18.05(6.07:53.64)
	After 6 months	34 (79.07%)	8 (19.51%)	<0.001*	15.58(5.37:45.25)
Semen volume (mL)	After 3 months	2.37±0.78	2.01±0.58	0.223	0.362(-229: 0.953)
	After 6 months	2.41±0.78	2.49±0.73	0.797	-0.079(-0.165: 0.535)
Sperm concentration (million sperm/mL)	After 3 months	35 (13.75-82)	72 (62.75-89.25)	0.036*	37(8: 60)
	After 6 months	32.5 (13-72)	86. (76-106.75)	0.005*	54(20: 78)

\*Significantly different as P value ≤0.05, CI: Confidence interval, RR: Relative risk

[figure not shown]
Preserved ejaculation (after three and six months) were significantly higher in group 1 than group 2 (P value <0.001).

Semen volume (after three and six months) was insignificantly different between both groups.

[figure not shown]
Sperm concentration (after three and six months) was significantly lower in group 1 than group 2 (P value<0.05).

**Figure 17:** Preserved ejaculation of the studied groups.

**Figure 18:** Semen volume of the studied groups.

[figure not shown]
**Figure 19:** Sperm concentration of the studied groups.

[figure not shown]

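### Table 4's post-operative MSHQ-EjD comparison appears to cover only men who still ejaculated (35 vs 8, then 34 vs 8), not the 43 vs 41 in its header

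*Combined protocol and SAP*

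**What the plan says.** Ejaculation is one of three outcomes named under Aim of the work, with voiding and erectile function. The Follow up section plans the score for everyone: "All patients will be followed-up regularly at 3 and 6 months postoperatively with the IPSS, Qmax, PVR, IIEF-5Q, MSHQ-EjD Short Form". The Results section says of the 45 + 45 randomised men: "All allocated patients were followed-up and analyzed statistically".

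Table 4 is headed n=43 for Group 1 (ejaculation-preserving resection) and n=41 for Group 2 (standard resection). It carries no note that any row uses fewer men. Its rows are:

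- Before surgery: 12.42 ± 1.23 vs 10.98 ± 2.16, P < 0.001, difference and CI "1.44(0.708: 2.181".
- 3 months: 10.26 ± 1.42 vs 9.63 ± 1.77, P = 0.284, "0.632(-0.544: 1.808".
- 6 months: 10.62 ± 1.76 vs 10.38 ± 2.26, P = 0.741, "0.243(-1.232: 1.717".

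The text concludes that the score "was insignificantly different at three and six months postoperative between both groups".

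Table 10, under the same 43 vs 41 header, reports preserved ejaculation in 35 vs 8 men at 3 months and 34 vs 8 at 6 months. For the semen measures it says: "Semen volume (after three and six months) was insignificantly different between both groups" and "Sperm concentration (after three and six months) was significantly lower in group 1 than group 2".

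**The concern.** With SDs of about 1.4 to 2.3 and more than 40 men per arm, the post-operative intervals in Table 4 should be much narrower than those printed. An interval that is too wide for its stated n suggests that fewer men were analysed.

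If those men are the ones who still ejaculated, the comparison conditions on an outcome that arises after randomisation and differs sharply by arm (81% vs 20% at 3 months). Similar scores among ejaculators answer a different question from the effect of the technique in all treated men. A reader who takes the header and the sentence at face value would conclude that the two operations left ejaculatory function about equal across both groups, on one of the trial's stated aims.

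**Working it through.** **Inputs.** Means, SDs, differences, CIs and P values are from Table 4; candidate group sizes are from its header, from Results (45/45) and from Table 10. The test is the unpaired Student t-test named under Statistical analysis.

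**Formula.** Pooled variance s² = [(n₁−1)s₁² + (n₂−1)s₂²]/(n₁+n₂−2); SE = s·√(1/n₁ + 1/n₂); CI = difference ± t(0.975, n₁+n₂−2)·SE. The printed half-widths are (1.808 + 0.544)/2 = 1.176 at 3 months and (1.717 + 1.232)/2 = 1.4745 at 6 months.

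**Step 1: can the printed rows be reproduced?**

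| Visit | n₁/n₂ | SE | Half-width | 95% CI | P |
|---|---|---|---|---|---|
| 3 months | printed | – | 1.176 | −0.544 to 1.808 | 0.284 |
| | 43/41 | 0.349 | 0.695 | −0.063 to 1.327 | 0.074 |
| | 45/45 | 0.338 | 0.672 | −0.040 to 1.304 | 0.065 |
| | 35/8 | 0.582 | 1.176 | −0.544 to 1.808 | 0.284 |
| 6 months | printed | – | 1.4745 | −1.232 to 1.717 | 0.741 |
| | 43/41 | 0.441 | 0.877 | −0.634 to 1.120 | 0.583 |
| | 45/45 | 0.427 | 0.849 | −0.606 to 1.092 | 0.571 |
| | 34/8 | 0.730 | 1.475 | −1.232 to 1.718 | 0.741 |

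Against 43/41 the printed intervals are 1.176/0.695 = 1.69 and 1.4745/0.877 = 1.68 times as wide. A Welch test at 43/41 does not help (P = 0.076 and 0.585).

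**Step 2: is the method sound?** The same formula at 43/41 gives half-widths of 1.186 and 1.309 for post-operative IPSS (Table 2) and 1.101 and 1.319 for IIEF-5Q (Table 3), equal to the printed values. So 43/41 was the basis of those rows.

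**Step 3: could 35/8 and 34/8 be a coincidence?** I tried every pair from 3 to 45 per arm, allowing for rounding of the SDs. On CI width and P alone several other pairs fit, such as 12/27 or 28/9 at 3 months and 12/30 or 27/9 at 6 months. I then assumed that each man's score is a whole number and required the printed means and the three-decimal difference to fit as well. One pair is left at each visit:

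- 3 months: 359/35 − 77/8 = 10.257 − 9.625 = 0.632, as printed. At 43/41 the only totals giving the printed means are 441 and 395, and 441/43 − 395/41 = 0.622.
- 6 months: 361/34 − 83/8 = 10.618 − 10.375 = 0.243, as printed. At n = 43, 456/43 = 10.605 and 457/43 = 10.628, so 10.62 cannot occur. At n = 41, 425/41 = 10.366 and 426/41 = 10.390, so 10.38 cannot occur.

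These pairs match Table 10 at both visits, including the fall from 35 to 34 in Group 1.

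**Step 4: baseline row.** The difference 559/45 − 494/45 = 1.444 with 45/45 gives 0.708 to 2.181, as printed; the half-width is 0.736 at 45/45 and 0.758 at 43/41.

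**Step 5: semen volume (supporting only).** At 3 months 35/8 gives P = 0.225 (0.221 to 0.229 with SD rounding; printed 0.223), whereas 43/41 would give 0.018. At 6 months 34/8 gives 0.796 (0.793 to 0.798; printed 0.797), whereas 43/41 would give 0.633.

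**Step 6: what could the answer be in all followed men?** Men absent: 43 − 35 = 8 vs 41 − 8 = 33 at 3 months; 43 − 34 = 9 vs 33 at 6 months. Suppose, purely for illustration, that every absent man had the same 6-month score v. The difference is (361 + 9v)/43 − (83 + 33v)/41. The last row subtracts the whole baseline gap of 1.44, assuming that it also holds in the 43 and 41.

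| v | 1 | 5 | 8 | 10 | 10.7 | 11 |
|---|---|---|---|---|---|---|
| Difference | +5.8 | +3.4 | +1.6 | +0.4 | 0.0 | −0.2 |
| Less 1.44 | +4.3 | +1.95 | +0.2 | −1.0 | −1.4 | −1.6 |

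The last row crosses zero at about v = 8.3.

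**The case against.** **The restriction is an inference.** The document never says that only ejaculators were analysed, and the uniqueness of 35/8 and 34/8 needs whole-number scores, which it does not state. This stands as a limit on certainty. It does not rescue 43/41, which fails without that assumption.

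**The scores may never have been collected.** Men without antegrade ejaculation may not have completed the questionnaire. The fault would then be missing data and an unlabelled denominator, not a choice to drop men. This is possible; the sentence would still not compare the groups.

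**The result is non-significant at 43/41 too.** True of P = 0.074 and 0.583, but those values reuse the subset's means and SDs and do not estimate the result in all followed men.

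**The baseline mismatch is not special to Table 4.** Correct. Baseline IPSS and IIEF-5Q also fit 45/45 under a 43/41 header (P = 0.0127 and 0.592, printed 0.013 and 0.592). It is a general header fault and no evidence of an ejaculator-only analysis. Likewise, 43/41 is itself short of the randomised 45/45.

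**The scenario range is speculative.** Agreed. A common score in both arms is unsupported, and subtracting the full gap is not a regression adjustment. The range shows only that neither size nor direction can be recovered.

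**Semen volume fits imperfectly.** The printed 6-month lower limit of −0.165 does not match the −0.692 from 34/8, although the upper limit does (0.535 vs 0.534). It looks like a misprint, so this row is secondary support.

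**Table 10 already reports ejaculation on 43 vs 41.** This limits the harm but does not make Table 4's sentence correct.

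**Conclusion.** The concern holds and must be fixed. Table 4's post-operative rows are not results for 43 vs 41 men. They reproduce to within 0.001 at the preserved-ejaculation counts at both visits, so the stated lack of difference between groups is, very probably, a comparison of 35 vs 8 and then 34 vs 8 men selected by a consequence of the surgery. About 80% of Group 2 (33/41) and 19% to 21% of Group 1 (8/43, 9/43) are absent.

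That the header is wrong for these rows rests on arithmetic alone. That the men analysed are the ejaculators rests on the match to Table 10, and its uniqueness on whole-number scores. The effect on the score in all followed men is unknown, and no direction is claimed. The preserved-ejaculation counts are not affected. Semen volume and sperm concentration share the unstated n. Sperm concentration can be measured only in men who ejaculate, so its fault is the missing n and the between-arm reading.

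**What to change.** **Required; no new data needed**

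1. Print the true n on every row of Table 4, and on the semen-volume and sperm-concentration rows of Table 10.
2. Have the investigators confirm which men were scored, then replace the sentence. If the inference is confirmed, for example: *Among men with preserved ejaculation (35 vs 8 at 3 months, 34 vs 8 at 6 months), MSHQ-EjD was 10.26 vs 9.63 and 10.62 vs 10.38; this does not compare the randomised groups.*
3. Label the ejaculator-only score, semen-volume and sperm-concentration results as descriptive, not as effects of technique.
4. Let preserved ejaculation on 43 vs 41 carry the between-arm conclusion. Its ratio needs relabelling first: the 18.05 printed as a relative risk is an odds ratio, (35 × 33)/(8 × 8); the risk ratio is (35/43)/(8/41) = 4.17.

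**Conditional on the data**

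5. If post-operative scores exist for men without antegrade ejaculation, compare all followed men (43 vs 41), adjusted for baseline MSHQ-EjD because the groups differed before surgery. This is a re-run.
6. If they do not exist, one rank-based analysis with every non-ejaculator at the worst rank is possible. Do not mix recorded and assigned scores, and state that it largely repeats the preserved-ejaculation result. That overlap is its main drawback.
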